#### 17.1.6. ADVERSE EVENTS OF SPECIAL INTEREST

Summaries of Thromboembolic or Hemolysis events will be presented by SOC and PT. Thromboembolic and Hemolysis Events are indicated on the eCRF.

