3.8.2.1 Overview of Screening, Treatment, and Post Infusion Follow-up Phases

All subjects will start their participation in the study upon the signing of the informed consent form (ICF). If applicable, a legally authorized representative may provide informed consent on behalf of the subject (see Section 7.4).

Eligible subjects based on Screening evaluations will complete the Baseline assessments, thereby initiating the Treatment. Subjects will continue with assessments for 45 weeks, with scheduled assessments at Week 0 (Visit 1) (Baseline, post-Baseline, and loading infusion over 2 days), followed by assessments and maintenance dosages every 3 weeks through Week 36 (Visit 13). The protocol-specified CS tapering will commence at Week 9 (Visit 4) and continue through Week 36 (Visit 13), inclusive, in conjunction with continued maintenance dosages of IP. Safety/Follow-up assessment visits are scheduled for Weeks 39, 42, and 45 (Visits 14, 15, and 16). Visits/procedures and assessments should be scheduled at the protocol-specified study day ± 3 days.

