4.3.6 Hemolysis

Procedures for hemolysis detection are provided in Appendix 8. In the event that true hemolytic anemia develops, it will be considered an AE and/or an SAE depending on whether seriousness criteria are met. Hemolytic ARs are defined as temporally associated with the study drug within 7 days post infusion.

4.4 Procedures for Eliciting Reports of and for Recording and Reporting Adverse Events and Intercurrent Illnesses

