Appendix 8 Hemolysis Detection

Schedule of the Procedures:

Study visit	Blood testing	Urine testing	Clinical parameters
Baseline (Week 0/prior to randomization)	X	X	X
End of first IP loading dose	X	X	X
At the time when last loading infusion is complete ^a	X	X	X
Weeks 3, 6, and 24 following completion of each maintenance infusion dosage ^a	X	X	X

Hemolysis evaluation (laboratory parameters) will also be performed 7 days post loading dose infusion at Baseline (Week 0) and 7 days post study drug infusion at Weeks 3 (Visit 2), 6 (Visit 3), and 24 (Visit 9).

Description of the procedures:

For the detection of hemolysis, the following procedure will be carried out to all the study population:

- 1. Blood testing: whole blood Hb, serum free Hb, haptoglobin, LDH, DAT, ARC, RBC, hematocrit, TBL and indirect bilirubin, and blood smear.
- 2. Urine testing: urinary sediment and hemoglobinuria.
- 3. Clinical parameters including red/dark urine, jaundice, as well as other signs and symptoms of anemia (such as pallor or tachycardia).

Definition of hemolysis associated with the use of IGIV-C:

In this clinical trial, an IVIg-associated hemolytic reaction is one in which there is evidence of a new hemolytic process [58]. Consideration of possible hemolysis as defined below should only be triggered if other explanatory factors/conditions can be excluded. Subjects from this study may be severely ill and may have anemia for a number of reasons. Therefore, it is important to exclude the underlying conditions and concomitant medications as a cause of anemia. The exclusions are:

- History or examination consistent with an alternative cause of anemia including blood loss (e.g. frequent phlebotomy is highly associated with changes in Hb and hematocrit levels for patients admitted to an internal medicine service [59,60]), iron-deficiency anemia, other drug-induced hemolytic anemia, or anemia associated with an underlying disease (e.g. autoimmune hemolytic anemia [61,62]).
- Negative DAT.

Absence of other inclusion criteria, in particular absence of evidence for hemolysis.

Potential events would require the following laboratory signs to be present (with the above caveats):

1. Drop in whole blood Hb of \geq 10 g/L*

AND

2. Positive DAT

AND

3. At least 2 of:

-	increased ARC*	-	hemoglobulemia
-	increased LDH level*	-	hemoglobinuria
-	significant spherocytosis	-	low haptoglobin level*
-	unconjugated hyperbilirubinemia		_

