### 17.2. LABORATORY EVALUATIONS

#### 17.2.1. CHEMISTRY, HEMATOLOGY, AND HEMOLYSIS

Results from the central laboratory will be included in the reporting of this study for clinical laboratory assessments (chemistry and hematology) parameters.

Presentations will use SI Units.

Quantitative laboratory measurements reported as "< X", i.e. below the lower limit of quantification, or "> X", i.e. above the upper limit of quantification, will be converted to X for the purpose of quantitative summaries, but will be presented as recorded, i.e. as "< X" or "> X" in the listings.

The following summaries will be provided for laboratory data:

- Actual and CFB by visit (for quantitative measurements)
- Shift from baseline according to normal range criteria (for quantitative measurements and categorical measurements with normal ranges)

Results out of normal range will be flagged in the listings.

For selected analytes, tabular summaries and listings will be provided for treatment-emergent laboratory abnormalities, utilizing the following thresholds of interest. Note that thresholds are in some cases relative to the established reference range (multiples of lower limit of normal [LLN] or upper limit of

---

Document: CCI

Author: PPD

Version Number:

Version Date:

Final 2.0  
12Apr2019

Template No: CCI

Effective Date: 01Apr2016

Reference: CCI

Copyright © 2009, 2010, 2012, 2016 CCI. All rights reserved.

The contents of this document are confidential and proprietary to CCI. Unauthorized use, disclosure or reproduction is strictly prohibited.

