## Analysis Plan

normal [ULN]) and in other cases are relative to an absolute value threshold:

- Hemoglobin: treatment-emergent (TE) value 8.9 g/dL or less AND a decrease of 1 g/dL from Baseline
- Absolute Neutrophils will have two thresholds:
  - o TE Neutrophils <750/mm^3
  - o TE Neutrophils < 500/mm^3
- Creatinine: TE > 2.5 x ULN (reference range specific to gender/age)
- Alanine aminotransferase [ALT]: TE > 3 x ULN (reference range specific to gender/age)
- Total bilirubin: TE > 3 x ULN (reference range specific to gender/age)
- Haptoglobin: < LLN

Hemolysis labs from the central laboratory will also be analyzed with methods similar to routine chemistry and hematology labs.

A listing of subjects with positive direct antiglobulin (DAT) test results will be provided. Subjects with positive DAT results are defined as those having a positive result for at least one of IgG and C3 from Screening through end of study. The listing will include all DAT results for any subject with at least one positive DAT value and will also include all hemoglobin, absolute reticulocyte count, serum free hemoglobin, haptoglobin, lactate dehydrogenase, and total and indirect bilirubin values at corresponding time points. Blood smear results (specifically "RBC morphology" whether there is presence of spherocytosis) and "urine blood" with any corresponding entries for "urine RBC/HPF" on urinalysis will also be included.

Serum pregnancy test results will be listed.

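### SAP 17.1.6 summarises hemolysis only from an eCRF flag that it does not tie to the Appendix 8 definition, and no by-arm count of subjects meeting the Appendix 8 laboratory criteria is planned

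*SAP*

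**What the plan says.** Hemolysis is a safety endpoint in its own right (Protocol 3.7 and 4.2) and an adverse event of special interest (Protocol 4.4.7.2). Protocol 3.8.3.2 sets up a dedicated central-laboratory programme: samples at baseline, around the loading dose, at the end of the Week 3, 6 and 24 infusions, and 7 days after the loading dose and each of those three infusions.

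Appendix 8 states the definition. It first asks for judgement: "Consideration of possible hemolysis as defined below should only be triggered if other explanatory factors/conditions can be excluded". It then says: "Potential events would require the following laboratory signs to be present (with the above caveats"). The first sign is "Drop in whole blood Hb of" at least 10 g/L. The second is a positive DAT. The third is any two of seven supporting findings.

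SAP 17.1.6 summarises thromboembolic and hemolysis events by SOC and PT, and gives the source of the classification in one sentence: "Thromboembolic and Hemolysis Events are indicated on the eCRF". It does not mention Appendix 8.

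SAP 17.2.1 adds by-visit and shift summaries, a listing of all subjects with any positive DAT, and a set of abnormality tables: "For selected analytes, tabular summaries and listings will be provided for treatment-emergent laboratory abnormalities, utilizing the following thresholds of interest". The hemoglobin entry reads: "Hemoglobin: treatment-emergent (TE) value 8.9 g/dL or less AND a decrease of 1 g/dL from Baseline".

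**The concern.** A trial that defines an event by laboratory criteria, and draws dedicated blood samples to detect it, would be expected to report how many subjects in each arm met those criteria. This SAP reports only what sites flagged, and does not say what rule the sites were to follow. Two sites could handle the same laboratory picture differently, and nothing in the planned output would show it.

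At stake is the reader's ability to compare the arms on a named safety endpoint of the active product. Without a derived count, an unblinded reader would have to build one from a listing, choosing cut-offs after seeing treatment assignment. The SAP does write out explicit criteria elsewhere: SAP 16.3.1.6 gives a four-part rule for identifying myasthenic crisis or MG worsening that needs inpatient care.

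**Working it through.** The plan states no hemolysis figure to reproduce, and no sample-size or power figure enters. The check compares each planned output with what Appendix 8 requires.

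**Step 1. The criteria.** Hb fall of at least 10 g/L (10 / 10 = 1.0 g/dL), with no absolute Hb level; AND positive DAT; AND at least 2 of 7 (raised reticulocytes, raised LDH, spherocytosis, unconjugated hyperbilirubinemia, free hemoglobin in blood, hemoglobinuria, low haptoglobin). Only the Hb fall has a numeric cut-off.

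**Step 2. The planned outputs.**

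| Output | What it gives | Count by arm of subjects meeting the combined criteria? |
|---|---|---|
| SAP 17.1.6 summary | Events flagged on the eCRF, by SOC and PT | No; link to Appendix 8 not stated |
| SAP 17.2.1 by-visit change and shift tables | One analyte at a time | No |
| SAP 17.2.1 Hb and haptoglobin thresholds | One analyte at a time | No |
| SAP 17.2.1 DAT listing | Essentially all components, per subject | No; a listing, entered by any positive DAT from Screening on, so new and pre-existing positivity are mixed |

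**Step 3. Could the Hb threshold stand in?** The fall needed to meet it is max(1.0, baseline − 8.9) g/dL.
- Baseline 9.9: max(1.0, 1.0) = 1.0 g/dL, the same as Appendix 8.
- Baseline 11 (illustrative): max(1.0, 2.1) = 2.1 g/dL.

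Above a baseline of 9.9 g/dL, a fall of exactly 1.0 g/dL meets the Appendix 8 Hb element but does not enter this table. The table therefore cannot replace the count. The difference does not measure missed hemolysis, because the threshold was not written to detect hemolysis.

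**Step 4. The recording rules behind the flag.** Protocol 4.3.6 makes an AE of true hemolytic anemia. Protocol 4.4.7.2 makes an AE of hemolysis, and mentions serious hemolytic anemia only as possible grounds for discontinuation. Protocol 4.3.4 turns an out-of-range result into an AE only if the investigator judges it clinically relevant. Both 4.3.6 and 4.4.7.2 point to Appendix 8, but they do not set the same recording threshold.

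**Step 5. A minor timing point.** Protocol 4.3.6 says: "Hemolytic ARs are defined as temporally associated with the study drug within 7 days post infusion". Protocol 3.8.2.1 says: "Visits/procedures and assessments should be scheduled at the protocol-specified study day ± 3 days". If that general window covers the 7-day sample, it may be drawn from day 7 − 3 = 4 to day 7 + 3 = 10, so days 8, 9 and 10 lie beyond the limit. The protocol does not say how a finding first seen on those days is classified. The SAP never uses the 7-day limit: it labels adverse reactions by definite causality (17.1.1.2), counts treatment-emergent events from the first infusion until the final visit (17.1) and applies no visit windows (6.5). No planned count changes.

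**The case against.** The strongest reply is that the eCRF flag may already be the Appendix 8 judgement. The protocol routes hemolysis through AE recording with reference to Appendix 8, and the Medical Monitor reviews reported AEs for possible hemolysis. Appendix 8 is also not a pure laboratory algorithm: other causes must be excluded, and the starred laboratory changes must lack another explanation and be clinically relevant. A derived table would be a broader screen than the full definition. Protocol 5.1.4 plans only to list the hemolysis laboratory results and flag abnormal ones, and the SAP already does more.

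Much of this stands. The documents do not show that the flag departs from Appendix 8, and a derived count must not be presented as confirmed hemolysis. But they do not show that the flag follows Appendix 8 either, and the recording rules differ. A count labelled as potential events and set beside the flag leaves the clinical judgement in place and makes any disagreement visible.

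A reader might infer three stronger things, none of which the documents support:
- **That hemolysis is counted from Hb of 8.9 g/dL or less.** That rule sits in a list with neutrophils, creatinine, ALT and bilirubin, and feeds no hemolysis count. An unflagged subject with a marked Hb fall would still enter the change-from-baseline and shift summaries and, if DAT-positive, the listing.
- **That the 7-day limit removes late samples or events.** It classifies reactions. Results from days 8 to 10 stay in the listings and nominal-visit summaries, and events stay among the TEAEs. A hemolysis found on day 9 may also have begun by day 7.
- **That these rules can only lower the count, mainly in the IGIV-C arm.** A flag can over-count as well as under-count, and nothing shows that blinded sites would under-report.

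**Conclusion.** The point holds as a gap in reporting. SAP 17.1.6 relies on a flag whose criteria it does not state, and no planned output gives, by arm, the number of subjects meeting the protocol's own laboratory criteria. No number can be put on the effect: the documents give neither an expected hemolysis rate nor the wording of the eCRF item. The conclusion rests only on what the two documents say about recording and tabulation. If the eCRF completion instructions, which are not among these documents, apply Appendix 8, the missing link could be closed with one sentence, but the by-arm laboratory count would still be absent.

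It is worth correcting because safety reporting here is descriptive, and the count uses data already collected. The mismatch between the 7-day limit and the ±3-day window is a matter of clarity and would not justify a change on its own.

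**What to change.** 1. In SAP 17.1.6, state how the eCRF hemolysis indication relates to Appendix 8.
2. In SAP 17.1.6 or 17.2.1, add one table by arm, derived from central laboratory data, of subjects with an Hb fall of at least 10 g/L from pre-treatment, a newly positive DAT and at least two of the seven further signs. State how results from different sampling times are combined. Fix the cut-offs for the signs without a number (reticulocytes, LDH, haptoglobin, bilirubin, spherocytosis and the rest) before unblinding.
3. Label these subjects as potential events before clinical exclusion of other causes, and cross-tabulate them with the eCRF-flagged events.
4. Reconcile the recording rules in Protocol 4.3.6 and 4.4.7.2. As a minor item, also reconcile the 7-day limit in 4.3.6 with the general visit window for the 7-day sample.

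The cost is one extra table, a few sentences and the effort of agreeing cut-offs. No new data are needed. The table may show more potential cases than sites flagged, some with another explanation, so the labelling in item 3 is needed.

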### 17.2. LABORATORY EVALUATIONS

#### 17.2.1. CHEMISTRY, HEMATOLOGY, AND HEMOLYSIS

Results from the central laboratory will be included in the reporting of this study for clinical laboratory assessments (chemistry and hematology) parameters.

Presentations will use SI Units.

Quantitative laboratory measurements reported as "< X", i.e. below the lower limit of quantification, or "> X", i.e. above the upper limit of quantification, will be converted to X for the purpose of quantitative summaries, but will be presented as recorded, i.e. as "< X" or "> X" in the listings.

The following summaries will be provided for laboratory data:

- Actual and CFB by visit (for quantitative measurements)
- Shift from baseline according to normal range criteria (for quantitative measurements and categorical measurements with normal ranges)

Results out of normal range will be flagged in the listings.

For selected analytes, tabular summaries and listings will be provided for treatment-emergent laboratory abnormalities, utilizing the following thresholds of interest. Note that thresholds are in some cases relative to the established reference range (multiples of lower limit of normal [LLN] or upper limit of

---

Document: CCI

Author: PPD

Version Number:

Version Date:

Final 2.0  
12Apr2019

Template No: CCI

Effective Date: 01Apr2016

Reference: CCI

Copyright © 2009, 2010, 2012, 2016 CCI. All rights reserved.

The contents of this document are confidential and proprietary to CCI. Unauthorized use, disclosure or reproduction is strictly prohibited.

## Analysis Plan

normal [ULN]) and in other cases are relative to an absolute value threshold:

- Hemoglobin: treatment-emergent (TE) value 8.9 g/dL or less AND a decrease of 1 g/dL from Baseline
- Absolute Neutrophils will have two thresholds:
  - o TE Neutrophils <750/mm^3
  - o TE Neutrophils < 500/mm^3
- Creatinine: TE > 2.5 x ULN (reference range specific to gender/age)
- Alanine aminotransferase [ALT]: TE > 3 x ULN (reference range specific to gender/age)
- Total bilirubin: TE > 3 x ULN (reference range specific to gender/age)
- Haptoglobin: < LLN

Hemolysis labs from the central laboratory will also be analyzed with methods similar to routine chemistry and hematology labs.

A listing of subjects with positive direct antiglobulin (DAT) test results will be provided. Subjects with positive DAT results are defined as those having a positive result for at least one of IgG and C3 from Screening through end of study. The listing will include all DAT results for any subject with at least one positive DAT value and will also include all hemoglobin, absolute reticulocyte count, serum free hemoglobin, haptoglobin, lactate dehydrogenase, and total and indirect bilirubin values at corresponding time points. Blood smear results (specifically "RBC morphology" whether there is presence of spherocytosis) and "urine blood" with any corresponding entries for "urine RBC/HPF" on urinalysis will also be included.

Serum pregnancy test results will be listed.

### 17.2.2. D-DIMER AND WELLS SCORE

D-dimer and Wells Score are collected for thromboembolism evaluation. D-dimer results are included in the laboratory data. The Wells Score data is collected on the eCRF. D-dimer and total scores of the Wells Score for Deep Vein Thrombosis and Pulmonary Embolism will be summarized with number of subjects, mean, standard deviation (SD), median, minimum, and maximum values. Summaries will be presented for actual and CFB by treatment and visit. All D-dimer and Wells Score data will also be presented in data listings.

### 17.2.3. VIRUS SAFETY TESTING

Blood samples for virus safety (viral nucleic acid amplification technology [NAT] and viral serology) testing will be collected at Baseline/Week 0 (Visit 1) prior to randomization, but will be tested only if the subject exhibits clinical signs and symptoms consistent with hepatitis A, hepatitis B, hepatitis C, human immunodeficiency virus (HIV), or parvovirus B19 infection while participating in the study. These samples will be retained until all analyses in support of the study are complete. Additional blood samples for viral NAT and viral serology may be collected and tested only if the subject exhibits clinical signs and symptoms consistent with hepatitis A, hepatitis B, hepatitis C, HIV, or parvovirus B19 infection while participating in the study.

Document: CCI

Author: PPD

Version Number:

Final 2.0

Version Date:

12Apr2019

Template No: CCI

Reference: CCI

Effective Date: 01Apr2016

Copyright © 2009, 2010, 2012, 2016 CCI. All rights reserved.

The contents of this document are confidential and proprietary to CCI. Unauthorized use, disclosure or reproduction is strictly prohibited.

---

**Analysis Plan**

---

If any virus safety testing was conducted, all available results will be listed.

**17.2.4. LABORATORY REFERENCE RANGES**

Quantitative laboratory measurements will be compared with the relevant laboratory reference ranges in standard international (SI) units and categorized as:

- Low: Below the lower limit of the laboratory reference range.
- Normal: Within the laboratory reference range (upper and lower limit included).
- High: Above the upper limit of the laboratory reference range.

**17.3. VITAL SIGNS**

The following Vital Signs measurements will be reported for this study:

- Systolic Blood Pressure (mmHg)
- Diastolic Blood Pressure (mmHg)
- Heart Rate (beats/min)
- Respiratory Rate (breaths/min)
- Temperature (°C)

Weight (kg) will be presented in listings and summarized with other vital signs.

The following summaries will be provided for vital signs data:

- Actual and CFB by visit

**17.4. PHYSICAL EXAMINATION**

Full physical assessment findings will be summarized with numbers and percentages by body system. Entries for 'Other' body systems will be grouped together; a subject with 2 or more 'Other' entries will be counted only once. Physical assessment change findings will be summarized with numbers and percentages per category of the change findings. Physical examination findings (normal and abnormal) with specific findings observed will be listed for each subject.

There are 7 body habitus/cushingoid features related to CS side effects assessed on the CS-related Physical Assessment Findings page of the eCRF. Each feature will be graded as absent [0], mild [1], moderate [2] or severe [3]. The data will be summarized by treatment and visit as well as presented in a listing. Correlation between the body habitus/cushingoid features and CS dose reduction will be

---

Document: CCI

Author: PPD

Version Number:

Version Date:

Final 2.0  
12Apr2019

Template No: CCI

Effective Date: 01Apr2016

Reference: CCI

Copyright © 2009, 2010, 2012, 2016 CCI. All rights reserved.

The contents of this document are confidential and proprietary to CCI. Unauthorized use, disclosure or reproduction is strictly prohibited.

---

**Analysis Plan**

---

explored in Section 16.3.3.3.

## 17.5. WHO-FIVE (WHO-5) WELL-BEING INDEX

The total score of WHO-5 Well Being Index (Appendix 7) is the sum of all 5 items reported on the WHO-5 page of the eCRF. Each item is scored from 0 to 5 (higher scores mean better well-being). The total score, ranging from 0 to 25, are reported on the eCRF and will not be recalculated. If one or more individual scores are missing, the WHO-5 total score will be reported as missing.

The total score will be summarized by treatment and visit. Both the total score and each individual score will also be presented in a listing. Correlation between the WHO-5 total score and CS dose reduction will be explored in Section 16.3.3.3.

---

Document:

Author:

CCI

PPD

Version Number:

Version Date:

Final 2.0  
12Apr2019

Template No: CCI

Effective Date: 01Apr2016

Reference: CCI

Copyright © 2009, 2010, 2012, 2016 CCI. All rights reserved.

The contents of this document are confidential and proprietary to CCI. Unauthorized use, disclosure or reproduction is strictly prohibited.

